1. Developing a novel technology-based intervention for anxiety and depressive symptoms among those receiving medication treatment for OUD.
2. Evaluating the feasibility of a technology-based intervention for anxiety and depressive symptoms among persons receiving treatment for OUD.
3. Evaluating the efficacy of a technology-based intervention for anxiety and depressive symptoms among persons with OUD.
4. Evaluating the efficacy of a technology-based intervention treating anxiety and depressive symptoms on cravings and opioid use among persons receiving medication treatment for OUD.

2. Objectives and Hypotheses

Aim 1: To test the feasibility and acceptability of the digital intervention designed to treat anxiety and depressive symptoms among persons receiving medication treatments for OUD.

Hypothesis 1: The digital intervention will show feasibility based on the ability to recruit participants (N = 40 within the digital intervention + medication treatment, N = 40 with medication treatment) and demonstrate acceptability of the application with greater than 50% of the intervention sessions completed on average by the treatment group.

Aim 2: To test the efficacy of a digital intervention targeting anxiety and depressive symptoms among persons receiving medication treatment for OUD. Sixty participants receiving medication treatment for OUD will be randomized to receive a digital intervention to treat anxiety and depression (N = 30) or care as usual (N = 30) for a total of four weeks.

Hypothesis 2: The digital intervention app group will experience (a) greater symptom reduction in anxiety and depressive symptoms (based on self-report measures) and (b) decreased opioid cravings and use across a four-week period (based on self-report measures and urine tests).

3. Study Design

Describe all study procedures, materials, and methods of data collection:

Recruitment. A population of 3000 adults who are receiving medication treatment for OUD will be recruited from an online study based on Google Adwords and Facebook advertisements as online recruitment has been shown to be a viable and cost-effective recruitment method for opioid users (Marshall et al., 2018).

We would also like to expand our recruitment efforts to Reddit sub-pages as well. Previous researchers looking at opioid addiction have had success posting in the Reddit forums and we would like to also recruit using this platform.

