Main Study: Participants will complete the main consent form. Participants will complete self-report assessments on their anxiety symptoms, depressive symptoms, opioid cravings, and opioid use behaviors. Participants will be randomized to a smartphone-based digital intervention or waitlist control condition. The control group can receive the intervention once they have completed the one-month follow up section of the study if they would like it. The digital intervention will be designed to treat participants' anxiety and depressive symptoms, and participants will be asked to use the intervention four times per week for four weeks (16 digital sessions). Participants will complete post measures and one-month follow-up measures on anxiety symptoms, depressive symptoms, opioid cravings, and opioid use behaviors. The Precision Dx12-panel test cups (manufactured by American Screening Complete Drug Test Solutions) will be mailed to participants. Participants will also be asked to complete five urine tests to detect substance use (amphetamines, barbiturates, benzodiazepines, cocaine, ecstasy, marijuana, methamphetamine, opioids, oxycodone, and propoxyphene) across the study (1 at pre-digital intervention, 1 during the digital intervention, 1 post-digital intervention, 1 between post and follow-up of the digital intervention, and 1 at the 1-month follow-up of the digital intervention). Participants will be instructed when to complete each urine test and will be asked to take a photo of the back the label of each test showing the results to the experimenters and to text these photos to a Google Voice Number maintained by the experimenters. Both the digital intervention group and the control group will receive the same follow-up assessments and be asked for the urine samples. Following the study, the control group will be able to access the intervention and have access to the study team for support.

The Link for the intervention videos is below:

<https://drive.google.com/drive/folders/1aGv-d85VnuriTcta9dkRt6OjizcMHRf2?usp=sharing>

4. Analysis

Describe any qualitative tests and measures as well as quantitative methods:

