Analyses. To test feasibility for **Hypothesis 1**, we will determine whether we can achieve the targeted enrollment ($N = 80$) and whether the average number of digital sessions is significantly higher than 50% based on multilevel binomial test nesting individual session completion rates within persons. To test **Hypothesis 2**, the current proposal will use intent-to-treat analyses employing multilevel modeling to examine moderation of change across time from pre to post, and post to follow-up. Based on power analyses, we will be well-powered to test the effects of the intervention (3-5 data points per person \times 80 participants = 180-300 \times 80% adherence = 144-240 data points total).

5. Study Progress Monitoring

Note: appropriate monitoring may include periodic assessment of the following:

- data quality
- timelines
- recruitment and enrollment

Provide a description of the methods which will be used to determine the progress of the study, including periodic assessments of data quality, timelines, recruitment, and enrollment as appropriate:

Recruitment. A population of 3000 adults who are receiving medication treatment for OUD will be recruited from an online study based on Google Adwords advertisements as online recruitment has been shown to be a viable and cost-effective recruitment method for opioid users (Marshall et al., 2018). We are only recruiting from the US.

We will also recruit via Reddit forum as well. Please see the document with the example of the post we would be planning on using.

Six opioid-focused subreddits were initially identified. Subreddits were selected based on their topical focus and their popularity. All were devoted to discussion of opioid use or recovery. In September 2019, the number of Redditors subscribed to each subreddit ranged from 4,000 to 82,000 people. Each subreddit was monitored by multiple moderators, who ensured all posts follow the Reddit community guidelines and remain focused on the topic of interest. All moderators in each of the six subreddits will be contacted by the study team to obtain approval to post the survey description and hyperlink. Moderators will be sent a study information sheet and a link to view the study description.

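### Hypothesis 2 tests efficacy on four or five outcomes over two intervals with no primary outcome, success rule or error control, so the chance of a false positive favouring the intervention is about 8-23% rather than 2.5%

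*Combined protocol and SAP*

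**What the plan says.** All references are to the combined protocol and SAP.

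- **Section 2, Objectives and Hypotheses.** Aim 2 is a test of efficacy. Hypothesis 2 predicts "greater symptom reduction in anxiety and depressive symptoms (based on self-report measures) and (b) decreased opioid cravings and use across a four-week period". Part (b) is to be judged "based on self-report measures and urine tests", so opioid use has two sources.
- **Section 3, Study Design, Procedure.** "Participants will complete post measures and one-month follow-up measures on anxiety symptoms, depressive symptoms, opioid cravings, and opioid use behaviors". Pre-treatment self-report assessments cover the same four constructs. Urine is tested five times.
- **Section 4, Analysis, Analyses.** Hypothesis 2 is to be tested by intent-to-treat "multilevel modeling to examine moderation of change across time from pre to post, and post to follow-up". On power, the plan says: "Based on power analyses, we will be well-powered to test the effects of the intervention". The support offered is a count of data points.

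No section names a primary outcome, a primary interval, an alpha level, sidedness, a multiplicity adjustment or a testing order. None says whether Hypothesis 2 is supported when one outcome improves or only when all do. The Analyses paragraph is complete as printed, so these gaps are not due to redaction or lost text.

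**The concern.** A trial that sets out to test efficacy needs a rule, fixed before the data are seen, for what counts as success. Here four constructs, or five outcomes if self-reported and urine-detected use are scored separately, are each examined over two intervals. That makes eight or ten tests. The plan ranks none of them and limits the error on none.

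Run as written, a single significant result among them could be reported as support for Hypothesis 2. A primary outcome chosen after the results are known would not repair this. At stake is how much weight a positive finding under Aim 2 can carry.

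**Working it through.** **The plan's own figure.** The only numbers near this point are the data-point counts in the Analyses paragraph. From the stated inputs, 80 × 3 = 240 and 80 × 5 = 400; at 80% adherence these become 192 and 320. The printed 180-300 and 144-240 follow only from 60 participants (60 × 3 = 180, 60 × 5 = 300; × 0.8 = 144 and 240). Either way this is a count of observations. It gives no alpha, effect size or error rate, so there is no stated error rate to reproduce.

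**Inputs from the documents.** Outcomes k = 4 or 5 (Hypothesis 2). Intervals = 1 if only the four weeks in Hypothesis 2 count, or 2 as in the Analyses paragraph. The direction is in favour of the intervention ("The digital intervention app group will experience (a) greater symptom reduction").

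**Assumptions, because the documents are silent.** Two-sided 0.05 per test. Between-outcome correlation r = 0 to 0.5. Equal within-person correlation ρ across the three times. Each contrast is treated as a normal test statistic.

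**Step 1, independent tests.** The chance of at least one false significant result in m tests is 1 − 0.95^m. The chance of at least one favouring the intervention is 1 − 0.975^m.

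- m = 4: 18.5% and 9.6%
- m = 5: 22.6% and 11.9%
- m = 8: 33.7% and 18.3%
- m = 10: 40.1% and 22.4%

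**Step 2, allowing for correlation.** The two change scores share the post measurement. Each has variance 2(1 − ρ) and their covariance is −(1 − ρ), so they correlate at −0.5 whatever ρ is. Simulating the null with that structure gives:

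| Outcomes | r | Pre to post only: any significant | Pre to post only: favouring intervention | Both intervals: any significant | Both intervals: favouring intervention |
|---|---|---|---|---|---|
| 4 | 0 | 18.5% | 9.6% | 31.7% | 18.5% |
| 4 | 0.3 | 17.4% | 8.7% | 29.8% | 17.2% |
| 4 | 0.5 | 15.6% | 7.8% | 26.9% | 15.5% |
| 5 | 0 | 22.6% | 11.9% | 37.9% | 22.6% |
| 5 | 0.3 | 20.9% | 10.5% | 35.2% | 20.6% |
| 5 | 0.5 | 18.3% | 9.1% | 31.1% | 18.1% |

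A single two-sided test gives 5% in either direction and 2.5% in favour. The favourable-direction rate is therefore 7.8/2.5 ≈ 3 times nominal at the low end and 22.6/2.5 ≈ 9 times at the high end.

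**Step 3, the all-must-succeed reading.** If every outcome had 80% power, joint power over four or five independent outcomes would be 0.8⁴ = 41% or 0.8⁵ = 33%. Beyond that the answer depends on the assumed standardised effect d. With five pre-to-post outcomes, 40 per arm and r = 0.3, simulated joint power is about 7% at d = 0.4, 18% at d = 0.5, 38% at d = 0.6 and 80% at d = 0.8. The documents give nothing with which to choose among these.

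**The case against.** Four arguments on the other side deserve weight.

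1. **Direction.** A reader might take 27-38% as the chance of a false efficacy claim. The documents do not support that. Hypothesis 2 is directional, and the figure also counts significant results that favour control. The favourable-direction figure is 15-23%. This argument stands.

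2. **Number of tests.** Hypothesis 2 speaks of "decreased opioid cravings and use across a four-week period", so post to follow-up may be meant only as a look at maintenance. That is a fair reading and brings the favourable-direction error down to 8-12%. But the Analyses paragraph lists both intervals under the test of Hypothesis 2 ("examine moderation of change across time from pre to post, and post to follow-up") and gives them no separate role.

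3. **Conjunction.** The hypothesis joins its outcomes with *and*, so one could say that all must succeed and no inflation arises. The plan never states that rule. A reader might go on to conclude that joint power is about 20%. That figure needs d near 0.5, r near 0.3 and 40 per arm, none of which is given for this purpose, and Section 2 also gives 30 per arm.

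4. **Outcome-specific claims in an early study.** The hypothesis separates (a) from (b), the Innovation list separates symptom efficacy from craving and use, and the intervention is a prototype. If each claim is confined to its own outcome, each has its own error rate. It would therefore go too far to infer that the trial can give no interpretable answer to Aim 2. The point narrows but remains, because the plan does not commit to outcome-specific claims, and Aim 2 is stated as efficacy, apart from the feasibility aim.

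**Conclusion.** The point holds as a gap in the decision rule. The plan tests efficacy on four or five outcomes over two intervals, with no primary outcome or interval, no one-versus-all rule and no error control.

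On any reading in which one significant result suffices, error is well above nominal. It is about 16-23% (four or five tests) to 27-38% (eight or ten tests) in either direction, and about 8-12% to 15-23% in favour of the intervention, against 2.5% for one test. These figures rest on an assumed two-sided 0.05 per test and outcome correlation of 0 to 0.5; higher correlation would lower them. Joint power under an all-must-succeed rule cannot be derived, because the documents give no effect size, correlation or alpha.

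This should be corrected before analysis.

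**What to change.** In the Analyses paragraph of Section 4:

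- Name two primary tests: the arm-by-time contrast from pre to post on PHQ-9, and the same contrast on GAD-Q-IV analysed as a continuous score. Holm-adjust the pair at two-sided 0.05. GAD-Q-IV is the only anxiety measure the plan names. The Measures text describes it for diagnosis only, so its scoring should be stated.
- Label craving and opioid use (self-report and urine) as secondary, reported with 95% confidence intervals.
- Report post-to-follow-up contrasts as description of maintenance, with no efficacy claim attached.

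This follows the plan's own logic. Aim 2 names anxiety and depressive symptoms as the target, and the Significance section presents lower craving and use as a possible further consequence. It holds the family error for the two primary tests at no more than 5%.

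The cost is a few sentences, with no new data or participants. The first Holm step is at 0.025, and craving or use alone can no longer carry the efficacy claim. As an illustration at d = 0.5, outcome correlation 0.5 and 40 per arm, the chance of at least one primary success is about 66%, against about 61% for a single unadjusted test. The two are different success criteria.

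Separately, the 80 and 60 participant figures in Section 2 and the Analyses paragraph must be reconciled before any power statement is made.

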Availability of the Study Team. [name] will be available to discuss the study or any concerns about the study with participants if requested by the participant and/or postdoctoral fellow. [name] will be available in the event of a clinical emergency, and this availability will be clearly communicated orally and in writing to study participants. Participants will be given a letter from investigators with information such as how to reach the investigators in the event of a clinical emergency. Participants will be referred to a treatment resource or a higher level of care if needed (i.e., hospitalization). Participants will be referred to a higher level of care if there is evidence of (1) acute active suicidality with a plan and intent to take one's life within a delineated period of time (i.e. less than 1 year), (2) acute homicidally with a plan or intent to take another's life, or (3) likelihood that they could immediately cause severe bodily harm to themselves or others (see Clinical Referrals below).

Ability to Withdraw. Participants may be able to withdraw from the study due to a significantly deteriorating course (e.g., need for hospitalization) or if the PI or participant determines that staying in the study is not in the participant's best interest. All participants who withdraw will be provided referrals for treatment.

Quality Control of Online Screen Data. To exclude duplication and ensure validity, Qualtrics checks every IP address and uses unique and sophisticated digital fingerprinting technology that is continuously being improved. Qualtrics is committed to providing the highest quality data to their clients. Qualtrics will replace respondents who finish less than half of the median survey completion length. Qualtrics also provides clients the opportunity to review the results and contact the Qualtrics team to request responses that need to be replaced, should there be any quality issues.

Data Security. All data on phones, on the server, and in-transit (including data sent from the wearable device to the phone) will be encrypted using industry standards (based on a 2048-bit encryption key; only the server can decrypt the data; and the data are physically stored on Amazon S3 data center servers protected by armed guards). The data collection and server storage are both fully HIPAA compliant.

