- 1) \$15 dollars for completing one-month follow-up post measures
- 2) \$15 for providing fourth urine sample results (after 6 weeks)
- 3) \$15 for providing fifth urine sample results (after 8 weeks)

15. Privacy of Participants

Note: Methods used to obtain information about participants may have an effect on privacy. For example:

- Consent discussions or interviews held in public which concern sensitive subjects or behaviors
- Observations of behavior, especially illicit behavior, in quasi-public settings

Describe any activities or interactions which could lead to a breach of privacy and provide a plan to protect participant privacy:

All Participants data will be collected and stored under a unique identifier. Any files linking the participant information and their study data will be stored on a password protected Dartmouth server. Participants' privacy will be safeguarded by fully informed consent by informing participants what data will be collected, who will have access to this information, and how knowledge of how information collected will be utilized and disseminated (Ziegeldorf, García-Morchón, & Wehrle, 2014).

16. Confidentiality of Data

Note: Any person engaged in research collecting information that could cause financial, social or legal harm to participants may apply for a [Certificate of Confidentiality](#). Certificates of Confidentiality are issued by the National Institutes of Health (NIH) to protect identifiable research information from forced disclosure. They are intended to allow the investigator and others who have access to research records to refuse to disclose identifying information on research participants in any civil, criminal, administrative, legislative, or other proceeding, whether at the federal, state, or local level.

a. If disclosed, could any of the data collected be considered sensitive, with the potential to damage financial standing, employability, insurability, or reputation?

No Yes

If Yes, describe the data or information, the rationale for their collection, and whether a Certificate of Confidentiality will be obtained:

Since we are collecting data about opioid addiction and urine test results, these results could potentially damage employability, reputation, and insurability. The research team believes that creating no-cost, scalable interventions for populations suffering from opioid addiction is an important step in advancing treatment for this population.

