b. Describe the safeguards employed to secure, share, and maintain data during the study, addressing any of the following which may apply:

- Administrative, ie. coding of participant data
- Physical, ie. use of locked file cabinets
- Technical, ie. encrypted data systems

All data will be stored on a password protected Dartmouth server. We will use a two-document system. The coded identifier form will contain both the Study ID and any identifiable data from the participant. This data includes name, DOB, phone number, email, address and any other contact information collected during the study. This form will be destroyed at the end of the study. The second is the Data element form, which will contain any study information collected (pictures of the urine test results, assessments, and smart phone data)

c. Describe the plan for storage or destruction of data upon study completion:

Data will be preserved for the duration of the study. Once the study is completed the coded identifier form which is the document that connects the participant ID with their contact information will be destroyed. However, all data collected for the duration of the study will be kept indefinitely until it is no longer needed. All results will be stored on a password protected server which will only be accessed by study team members.

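### Urine-test photos are texted to a Google Voice number, a route that does not meet the plan's own promise that all data in transit are encrypted and readable only by the server

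*Combined protocol and SAP*

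**What the plan says.** **Transfer.** Section 3 (Main Study): "Participants will also be asked to complete five urine tests to detect substance use". For each test the participant photographs the label showing the result and is asked "to text these photos to a Google Voice Number maintained by the experimenters". Sections 9 and 13a repeat that pictures of the results are sent to the team. Neither adds a safeguard.

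**Encryption promise.** Section 6b (Data Security) covers "All data on phones, on the server, and in-transit", says that "only the server can decrypt the data" and that "the data are physically stored on Amazon S3 data center servers protected by armed guards", and declares both collection and server storage HIPAA compliant. It makes no exception for the photos.

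**Storage.** Section 16b: "All data will be stored on a password protected Dartmouth server". It describes two forms. The coded identifier form holds contact details, including the phone number. The data element form holds study data and names the urine-test pictures among them.

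**Harm.** Section 16a, on the opioid and urine-test data: "these results could potentially damage employability, reputation, and insurability". The form's prompt there also asks "whether a Certificate of Confidentiality will be obtained". The answer does not say.

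**The concern.** The photos show drug-test results, on a panel covering many substances, for people in treatment for opioid use disorder. The plan recognises what disclosure could cost them and makes a broad security promise. The step that moves these results from participant to study team does not appear to be covered by that promise, and nothing else in the plan covers it. If the procedure is followed as written, participants are offered a protection that is not delivered for data the plan itself calls potentially damaging. What is at stake is confidentiality and the accuracy of what the plan tells the ethics committee about it.

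**Working it through.** No statistical formula applies. The check sets the sections side by side and then counts the photos affected.

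**1. Does the text route meet the section 6b promise?**

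| Element of section 6b | Photo route in section 3 |
|---|---|
| All data encrypted in transit | Sent by text; no encryption or secure messaging is stated for this step |
| Only the server can decrypt | Sent to a number the experimenters maintain, so they read the result there |
| Held on Amazon S3 | First received in the account behind the number |
| Collection HIPAA compliant | No arrangement is described for this step |

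The second row is enough. A result that staff open in a messaging account is not something that only a server can decrypt. That follows from the plan's own words and needs no knowledge of the messaging service.

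**2. Is the receiving account a named storage place?** Section 6b names Amazon S3 and section 16b names a Dartmouth server. The account is neither. The plan does not say when photos leave it for the server, who codes them, or whether they are then deleted from it.

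**3. Does the two-form separation protect the photos at receipt?** Section 16b puts phone numbers in one form and urine-test pictures in the other. Assumption: a text arrives showing the sender's number. Identifier and result are then together from receipt until someone moves and codes the photo.

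**4. How many photos?**
- Tests per participant: 5 (section 3).
- At 60 participants (section 2, Aim 2): 60 × 5 = 300.
- Cups budgeted in section 13a: 12 cases × 25 = 300, which matches.
- Payment budgeted in section 13a: $7,200 / $120 per participant = 60 participants, which also matches.
- At 80 participants (section 10a; also section 2, Hypothesis 1, and section 4): 80 × 5 = 400.

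The purchase plan supports 300. The figure of 400 is an upper value that applies only if the larger target is met and more cups are bought.

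**The case against.** The strongest reply is that the Data Security paragraph was never about these photos. It mentions data passing from a wearable to the phone, an encryption key and cloud servers, which fits the passive-sensing app. Read literally, server-only decryption would also be breached by any data that staff open, including a photo uploaded to Qualtrics. On this view the fault is loose drafting, and narrowing one sentence would cure it.

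Much of this stands. The paragraph probably was written for passive sensing, and moving the photos to Qualtrics without rewording it would leave the literal conflict in place. But the text covers all data, and if its scope is narrower, the photos have no stated protection in transit at all. Either reading calls for a change.

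A reader might infer more than the documents support:

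- **That the messaging service is insecure, or keeps readable copies.** The plan says nothing about the account's type, security or retention. The point rests on a promise not met and a safeguard not described.
- **That section 16b is contradicted.** It is not. It governs storage and expressly includes the photos. The gap lies in the transfer and in any copies left behind.
- **That fear of exposure will keep positive results from being sent.** No passage supports this. Section 14 pays $15 per completed test with no condition on the result, and the same team would see the result by any route.
- **That a Certificate of Confidentiality is required.** The form says researchers may apply for one. It guards against forced disclosure and so does not bear on the text route.
- **That participants are not told of the text route in the consent form.** Consent pages are not in the material reviewed, so this cannot be judged.

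**Conclusion.** The point holds as a contradiction within the plan. The section 6b promise, as worded, is not met by the section 3 procedure for urine-test photos, and no other in-transit safeguard is given for data whose disclosure section 16a says could cause harm. About 300 photos are affected on the budgeted numbers, and up to 400 at N = 80.

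Two assumptions are involved. The first is that experimenters read the photos in the receiving account, which is the natural reading of section 3. The second, needed only for the point about result and identifier meeting, is that the sender's number is visible on receipt.

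This concerns participant protection. It does not touch the estimates, power or missing data. The change should be made because the safeguard is stated but not delivered and the remedy is inexpensive. Separately, and as a minor matter, section 16a leaves the certificate question unanswered.

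**What to change.** **Preferred.** Collect each photo by upload under study ID on Qualtrics, which already delivers the intervention and which section 4 describes as HIPAA compliant. Use text messages only as prompts. Reword Data Security in section 6b so that it states, for each data type (passive sensing, questionnaires, urine-test photos), how it is protected in transit, who can read it and where it is stored. The documents do not describe an upload function, so the team should confirm that one is available.

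**If texting is kept.** Limit the section 6b promise to the data it covers. Disclose the text route to participants. State how and when photos are moved to the Dartmouth server, how they are coded, and when they are deleted from the receiving account.

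**In either case.** Answer in section 16a whether a Certificate of Confidentiality will be obtained.

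**Cost.** One upload item for each of the five tests, and wording in sections 3, 6b and 16. Opening a link is slightly less convenient than replying to a text. If participants are asked to delete their own copy, they should do so only after receipt is confirmed, since a failed upload could otherwise lose the result.
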